8.2.5. Clinical Safety Laboratory Assessments

See [Appendix 2](#) for the list of clinical safety laboratory tests to be performed and the [SoA](#) for the timing and frequency. Confirmation of eligibility is required at Cycle 1 Day 1. All protocol-required laboratory assessments, as defined in [Appendix 2](#), must be conducted in accordance with the laboratory manual and the [SoA](#). For laboratory collection volumes see the laboratory manual. Unscheduled clinical laboratory measurements may be obtained at any time during the study to assess any perceived safety issues.

The investigator must review the laboratory report, document this review, and record any clinically relevant changes occurring during the study in the AE section of the CRF. Clinically significant abnormal laboratory findings are those which are not associated with the underlying disease, unless judged by the investigator to be more severe than expected for the participant's condition.

All laboratory tests with values considered clinically significantly abnormal during participation in the study or within 30 days (± 7 days) after the last dose of study intervention should be repeated until the values return to normal or baseline or are no longer considered clinically significant by the investigator or medical monitor.

If such values do not return to normal/baseline within a period of time judged reasonable by the investigator, the etiology should be identified and the sponsor notified.

See [Appendix 6](#) for suggested actions and follow-up assessments in the event of potential drug-induced liver injury.

No need to repeat a clinical laboratory assessments on Cycle 1 Day 1 if the baseline assessment was performed within 7 days prior to that date ([SoA](#)).

8.2.6. Pregnancy Testing

Pregnancy tests may be urine or serum tests, but must have a sensitivity of at least 25 mIU/mL. Pregnancy tests will be performed in WOCBP at the times listed in the [SoA](#). Following a negative pregnancy test result at screening, appropriate contraception must be commenced and a second negative pregnancy test result will be required at the baseline visit prior to the participant's receiving the study intervention. Pregnancy tests will also be done whenever 1 menstrual cycle is missed during the active treatment period (or when potential pregnancy is otherwise suspected) and at the end of the study. Pregnancy tests may also be repeated if requested by IRBs/ECs or if required by local regulations. If a urine test cannot be confirmed as negative (eg, an ambiguous result), a serum pregnancy test is required. In such cases, the participant must be excluded if the serum pregnancy result is positive.

If a participant requiring pregnancy testing cannot visit a local laboratory, a home urine pregnancy testing kit with a sensitivity of at least 25 mIU/mL may be used by the participant to perform the test at home, if compliant with local regulatory requirements. The pregnancy test outcome should be documented in the participant's source documents/medical records and relevant data recorded on the CRF. Confirm that the participant is adhering to the contraception method(s) required in the protocol.

8.2.7. Local Site Injection Tolerability Assessment

Assessments to monitor local tolerability to sasanlimab SC injections will be performed as outlined in the respective [SoA](#).

Any observed abnormality at the injection site will be judged by the investigator to determine whether a corresponding AE should be reported; otherwise details of these assessments will not be recorded on the CRF. When appropriate, at the discretion of the investigator, a participant with an ISR may be referred for a dermatological consultation and skin biopsy may be obtained for future examination of the ISR. If injection site reaction is noted, site tolerability assessments should continue until the symptoms resolve.

8.2.8. EOT Visit

Participants who discontinue study treatment will undergo the EOT visit and obtain assessments per the [SoA](#). The EOT assessments will be conducted at the visit that the participant is discontinued from study treatment or no longer than 1 week after the decision to discontinue the participant from study intervention and prior to the initiation of new anticancer therapy. The tumor assessments must be completed if not completed in the last 8 weeks and prior response is other than PD. Laboratory assessments must be completed if not completed in the prior 7 days.

If the EOT visit falls within 7 days of the 30-day follow-up visit, the EOT visit can be used to satisfy the requirements for both visits.

8.2.9. 30/60/90 Day Follow-Up Visit

The initial safety follow-up visit will be conducted in the clinic 30 days after last dose of study intervention. The 60-day and 90-day follow-up visits will be performed via remote contact (eg, telephone). The investigator may conduct these follow-up visits in clinic if any concerns are noted during the remote contact.

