ECG (standard 12lead)	X	See Table 2 , Table 3 and Table 4 .					X			See Section 8.2.4 for additional information.
Hematology	X	X		C1 & C2	X	C1	X	X	See Section 10.2 .	
Chemistry	X	X		C1 & C2	X	C1	X	X	See Section 10.2 .	
Coagulation	X	X		C1 & C2	X	C1	X	X	See Section 10.2 .	
Urinalysis	X	X					X	X	See Section 10.2 .	
Endocrinology: Thyroid function studies: T3, T4, TSH	X	C1D1, C4D1, then Q12W thereafter (and if clinically indicated).					X			If TSH abnormal, analysis of reflex free T4 and free T3 should be obtained. Supplementation is acceptable to achieve a TSH WNL. In participants with abnormal TSH, if free T4 and T3 are normal and participant is clinically euthyroid, participant is eligible.
Pregnancy test	X	X					X		WOCBP only.	
Viral disease screening	X								Subsequent HBV monitoring may be required per local practice for participants	

090177e198aafefApproved\Approved On: 22-Nov-2021 20:52 (GMT)

Table 1. Schedule of Activities (Part 1 and Part 2)

Visit Identifier	Screening	28 Day Treatment Cycle					EOT	30 day safety F/U	Long-term safety F/U	Notes:	
		Day 1	Day 2	Day 8	Day 15	Day 22					
Abbreviations used in this table may be found in Appendix 17 .	≤28						See notes	See notes		
 EOT and 30-day F/U see Sections 8.2.8 and 8.2.9 for timing of visits. See Section 8.2.9 for 60- and 90-day F/U. See Section 8.3.3 for follow-up AE and SAE assessments. 	
Visit Window (Days)		±2	—	±1	±1	±1		±3	±7	No Visit Window for C1D1. A 2-day Visit Window for Day 1 starts with Cycle 2.	
										who test positive for HBsAb and/or positive HBcAb.	
Safety Assessments											
Serious and nonserious AE monitoring	X	X	X	X	X	X	X	X	X	Includes injection site reaction on cycle for sasanlimab. See Sections 8.3 and 8.2.7 .	
Concomitant medication(s) monitoring	X	X	X	X	X	X	X	X		See Section 6.8 .	
Efficacy Assessments											
Serum tumor-associated marker(s)	X	X								Participants with defined serum tumor markers should continue monitoring on day 1 of each cycle.	
CT or MRI scans of chest, abdomen, pelvis, any clinically indicated sites of disease, and of bone	X	To be obtained every 8 weeks from C1D1 dose (±7 days)									See Section 8.1.1 .
Study Intervention and Other Treatments											
PF-07265028 administration		Continuous QD									See Section 6.1 . See SoA Table 2 , and Table 3 Table 4 .

090177e198aafefApproved On: 22-Nov-2021 20:52 (GMT)

Table 1. Schedule of Activities (Part 1 and Part 2)

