8.1. Efficacy Assessments

8.1.1. Tumor Response Assessments

Tumor assessments will include all known or suspected disease sites. Imaging will include contrast enhanced chest, abdomen and pelvis computed tomography or MRI scans; brain computed tomography or MRI scan for participants with known or suspected brain metastases; bone scan for participants with known or suspected bone metastases. For participants with known computed tomography contrast allergy, a non-contrast CT of the chest with contrast enhanced abdominal and pelvic MRI can be used. The same imaging technique used to characterize each identified and reported lesion at baseline will be employed in the following tumor assessments.

Anti-tumor activity will be assessed through radiological tumor assessments conducted at baseline, during treatment as specified in the [schedule of activities](#), whenever disease progression is suspected (eg, symptomatic deterioration), and at the time of withdrawal from treatment (if not done in the previous 4 weeks). Investigator (local) assessment of response will be made using RECIST version 1.1 and irRECIST (see [Sections 10.12](#) and [10.13](#)).

All participants' files and radiologic images must be available for source verification and for potential peer review.

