All sites of disease must be assessed at baseline. Baseline assessments should be done as close as possible prior to study start. For an adequate baseline assessment, all required scans must be done within 28 days prior to treatment and all disease must be documented appropriately. If baseline assessment is inadequate, subsequent statuses generally should be indeterminate.

Target lesions

All measurable lesions up to a maximum of 2 lesions per organ, 5 lesions in total, representative of all involved organs, should be identified as target lesions at baseline. Target lesions should be selected on the basis of size (longest lesions) and suitability for accurate repeated measurements. Record the longest diameter for each lesion, except in the case of pathological lymph nodes for which the short axis should be recorded. The sum of the diameters (longest for non-nodal lesions, short axis for nodal lesions) for all target lesions at baseline will be the basis for comparison to assessments performed on study.

- If 2 target lesions coalesce the measurement of the coalesced mass is used. If a large target lesion splits, the sum of the parts is used.
- Measurements for target lesions that become small should continue to be recorded. If a target lesion becomes too small to measure, 0 mm should be recorded if the lesion is considered to have disappeared; otherwise a default value of 5 mm should be recorded.

NOTE: When nodal lesions decrease to <10 mm (normal), the actual measurement should still be recorded.

Non-target disease

All non-measurable disease is non-target. All measurable lesions not identified as target lesions are also included as non-target disease. Measurements are not required but rather assessments will be expressed as ABSENT, INDETERMINATE, PRESENT/NOT INCREASED, INCREASED. Multiple non-target lesions in 1 organ may be recorded as a single item on the CRF (eg, 'multiple enlarged pelvic lymph nodes' or 'multiple liver metastases').

OBJECTIVE RESPONSE STATUS AT EACH EVALUATION (SEE Table 17)

Disease sites must be assessed using the same technique as baseline, including consistent administration of contrast and timing of scanning. If a change needs to be made the case must be discussed with the radiologist to determine if substitution is possible. If not, subsequent objective statuses are indeterminate.

Target disease

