2.1.2. Part 2 Primary Estimands

The treatment effect of PF-07265028 in combination with sasanlimab assessed by ORR using the RECIST version 1.1 and irRECIST in the analysis population.

- *Variable: Objective response defined as CR or PR according to RECIST v1.1 and irRECIST, from the date of first dose until the date of the first documentation of PD, death, or start of new anticancer therapy. Both CR and PR must be confirmed by repeat assessments performed no less than 4 weeks after the criteria for response are first met.*
- *Analysis population: The response evaluable set defined as all enrolled participants who received at least 1 dose of study treatment and had adequate baseline disease assessment. Participants who discontinued early or died will be included.*
- *Population-level summary measure: ORR defined as the proportion of participants in the analysis population with OR and 2-sided 95% CI for ORR using the Clopper-Pearson/Wilson method. Participants who do not have a post-baseline tumor assessment due to early progression of disease, who receive anti-cancer therapies other than the study treatments prior to reaching a CR or PR, or who die, have PD, or stop tumor assessments for any reason prior to reaching a CR or PR will be counted as non-responders in the assessment of OR.*

For the primary estimand of incidence of AEs, see [Section 2.1.1](#).

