6.2.3. Objective Response

In Part 1, objective response per RECIST 1.1 and irRECIST is a secondary endpoint. The proportion of participants with PR and irPR, as appropriate, will be derived.

- Analysis sets: Safety analysis set and response evaluable set, respectively.
- Analysis methodology:

Both confirmed ORR and unconfirmed ORR (uORR) will be determined based on the confirmed and unconfirmed CR and PR. ORR will be based on the best overall response (BOR) of a participant, according to RECIST 1.1 and irRECIST. In the BOR derivation, the minimum duration of SD as the best overall response is set as 5 weeks.

Unconfirmed CR (uCR) is defined as one objective status of CR documented before PD, while confirmed CR requires two objective statuses of CR a minimum of four weeks apart documented before PD. Sequences of CR - Non-evaluable - CR are considered confirmed CR as long as the two CR responses are observed at a minimum of 4 weeks apart. Similarly, unconfirmed PR (uPR) is defined as one objective status of PR documented before PD but not qualifying as uCR. Confirmed PR is defined as two objective statuses of PR or better (PR followed by PR or PR followed by CR) a minimum of four weeks apart documented before PD, but not qualifying as CR. Sequences of PR - Stable Disease or Non-evaluable - PR are considered PRs as long as the two PR responses are observed at a minimum of 4 weeks apart. Based on these definitions, the unconfirmed ORR analysis will include both confirmed CR or PR and unconfirmed CR or PR as responders, whereas the confirmed ORR analysis will only include confirmed CR or PR as responders.

Consider there may be some participants who cross over from Part 1A monotherapy to Part 1B combination therapy, two methods will be used for Part 1 ORR calculation. The primary one will only include (censor) the tumor response data by the cross over

date for those participants. The additional analysis will combine the participant who cross over from monotherapy to combination therapy with Part 1B participants for ORR calculation, in which only the tumor response data after the cross over date will be considered for the evaluation of best overall response. The re-baseline method may be considered if needed.

ORR and its 95% exact confidence interval as described in [Section 5.2.1](#) will be presented for each dose level and the total across all dose levels.

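### Protocol 8.1.1 and 8.2.8 set different look-back windows (4 versus 8 weeks) for the end-of-treatment tumor scan, so some first responses may never get a required confirming scan

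*Protocol*

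**What the plan says.** Protocol 8.1.1 (Tumor Response Assessments) lists the occasions for imaging beyond baseline and the regular schedule: "whenever disease progression is suspected (eg, symptomatic deterioration), and at the time of withdrawal from treatment (if not done in the previous 4 weeks".

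Protocol 8.2.8 (EOT Visit) covers the same scan: "The tumor assessments must be completed if not completed in the last 8 weeks and prior response is other than PD".

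The two sections differ in two ways. The look-back is 4 weeks in one and 8 weeks in the other, and only 8.2.8 drops the scan for participants already assessed as PD.

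The Schedule of Activities (Table 1) does not settle the matter. Its imaging row reads "To be obtained every 8 weeks from C1D1 dose (±7 days" and points to 8.1.1, while its note on the EOT visit points to 8.2.8.

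For the Part 2 primary endpoint, SAP 2.1.2 states "Both CR and PR must be confirmed by repeat assessments performed no less than 4 weeks after the criteria for response are first met". SAP 6.2.3, which 6.4.1 applies to Part 2, adds that "the confirmed ORR analysis will only include confirmed CR or PR as responders". The same section also reports an unconfirmed ORR.

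**The concern.** Scans are 8 weeks apart, so an 8-week look-back is usually satisfied by the last scheduled scan. A site working from the EOT visit section would then often omit a scan that a site working from the tumor assessment section would perform.

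The difference reaches a primary endpoint. Take a participant whose first PR is seen at a scheduled scan and who stops treatment six weeks later, for example for toxicity. Under 8.1.1 an EOT scan is due and can confirm the response. Under 8.2.8 alone no scan is required. I found no later scan in the schedule: follow-up after discontinuation is for safety up to 90 days, and the 60- and 90-day contacts are remote. The response then stays unconfirmed and counts as a non-response.

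Expansion cohorts have at most 40 participants, and Protocol 9.5.2 allows enrollment to stop after 15 if little activity is seen, so single responses carry weight.

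**Working it through.** The documents give no figure on this point to reproduce. The check uses their timings.

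**Inputs from the documents**
- Scan interval 56 days, window ±7 days (Table 1).
- Baseline scan 0-28 days old at first dose: "all required scans must be done within 28 days prior to treatment" (Appendix 12).
- EOT assessments 0-7 days after the decision to stop: "no longer than 1 week after the decision to discontinue the participant from study intervention" (8.2.8).
- Look-backs of 28 days (8.1.1) and 56 days (8.2.8).

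**Assumptions**
- All scheduled scans are done within window.
- The decision to stop falls evenly within a scan interval.
- Baseline scan age, scan timing within the window and EOT delay are uniform over their ranges.

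**Step 1: how often each rule triggers a scan.** Let A be the age of the last scan at the EOT visit.
- After the first on-treatment scan, exact schedule, no delay: P(A>28) = 28/56 = 0.50 and P(A>56) = 0.
- Adding a delay that averages 3.5 days: P(A>28) = 31.5/56 = 0.56 and P(A>56) = 3.5/56 = 0.06.
- Before the first on-treatment scan, baseline scan 14 days old on average, no delay: P(A>28) = 42/56 = 0.75 and P(A>56) = 14/56 = 0.25.

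A simulation of 1,000,000 draws reproduces these values and adds the ±7-day window:

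| Time of stopping | Timing | 4-week rule | 8-week rule |
|---|---|---|---|
| After first on-treatment scan | exact, no delay | 50% | 0% |
| After first on-treatment scan | ±7 days, delay up to 7 days | 56% | 7.6% |
| Before first on-treatment scan | exact, no delay | 75% | 25% |
| Before first on-treatment scan | ±7 days, delay up to 7 days | 81% | 31% |

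**Step 2: a different stopping pattern.** With exponential time on treatment (assumed median 8-26 weeks) and all discontinuations pooled, the 4-week rule triggers a scan in about 41-64%. The 8-week rule does so in about 0-8% if the baseline scan is on day 0, and about 5-17% if it is 0-28 days old.

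**Step 3: confirmations at stake.** Only stops 4-8 weeks after first response separate the two rules. Before 4 weeks neither triggers a scan; by 8 weeks the next scheduled scan is due. For an exponential time from first response to stopping with median m weeks, the share is 2^(-4/m) - 2^(-8/m).
- m = 12: 0.794 - 0.630 = 0.164
- m = 16: 0.134
- m = 26: 0.091
- m = 52: 0.948 - 0.899 = 0.049

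For an illustrative 6 initial responders in 40, that is 6 × 0.049 = 0.3 to 6 × 0.164 = 1.0 confirmations. One loss moves ORR from 6/40 = 15% to 5/40 = 12.5%. For scale, the exact 95% interval for 6/40 is 5.7% to 29.8%.

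The share who stop within 4 weeks, and have no EOT scan under either rule, is 1 - 2^(-4/m): 0.206 at m = 12 and 0.052 at m = 52.

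**Step 4: PFS.** SAP 6.5.1 censors participants without an event at the last adequate scan. Three provisions limit the loss. Protocol 8.1.1 requires a scan on suspicion of progression whatever the look-back. Appendix 12 asks sites to try to document progression after discontinuation. SAP Table 3 counts PD or death after at most one missed assessment as an event.

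**The case against.** The strongest reply is that both sentences require a scan and neither forbids one. A site that obeys both meets the 4-week rule and so, PD condition aside, the 8-week rule too. Data are lost only where 8.2.8 is read as excusing what 8.1.1 demands. That is correct, but nothing in the protocol says 8.1.1 prevails, and a site starting from the EOT note in Table 1 is sent to 8.2.8.

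The even-stopping assumption is also open to challenge. Treatment normally continues until confirmed PD, so many stops will follow closely on a scan, where neither rule triggers another. The percentages also compare the look-backs alone and ignore the PD exclusion in 8.2.8. They show how far the rules diverge; they do not forecast scan counts. Similarly, 5-16% is an upper bound on lost confirmations: a responder stopping because of progression would not be confirmed by an EOT scan, and some who withdraw would decline one.

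Three stronger readings are tempting, and the documents do not support them.
- A reader might infer that participants stopping for clinical deterioration are lost as PFS events. Protocol 8.1.1 names that situation as a reason to scan, independent of any look-back.
- A reader might infer that the 8-week rule almost never applies. That is fair after the first on-treatment scan but not before it, because the baseline scan may already be four weeks old at first dose.
- A reader might expect one or two of six responses to be lost, taking ORR to 10%. The stopping times examined give at most about one.

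**Conclusion.** The text is wrong as written: two current sections set different conditions for the same scan, and the schedule refers to both without ranking them. The divergence is large in scans required. Its effect on confirmed ORR is modest: under the assumed medians of 12-52 weeks from first response to stopping, at most about 5-16% of initial responders are affected, and only at sites that follow 8.2.8 alone. The unconfirmed ORR softens the consequence but is not the primary estimand. The study tests no hypothesis, so no error rate is involved.

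For PFS, what remains is unsuspected progression in participants who stop for another reason, plus earlier censoring. The documents do not allow this to be sized. The point should be corrected, but it does not threaten the design.

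**What to change.** State one look-back in Protocol 8.1.1, 8.2.8 and the imaging row of Table 1. The 4-week interval already in 8.1.1 is the natural choice because it matches the minimum gap for confirming a response.

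In the same edit, settle whether the scan is waived once PD has been recorded. Only 8.2.8 waives it, while irRECIST (Appendix 13) requires progression to be confirmed by imaging at least 4 weeks later. Changing the number alone would leave the sections inconsistent.

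The cost is a wording change in two sections and one table row. The 4-week window adds no scan that 8.1.1 does not already require; the effect of the PD condition depends on how it is resolved. Responders who stop within 4 weeks of first response will still have no EOT scan under this rule.

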8.3. Adverse Events, Serious Adverse Events, and Other Safety Reporting

The definitions of an AE and an SAE can be found in [Appendix 3](#).

AEs may arise from symptoms or other complaints reported to the investigator by the participant (or, when appropriate, by a caregiver, surrogate, or the participant's legally authorized representative), or they may arise from clinical findings of the Investigator or other healthcare providers (clinical signs, test results, etc.).

The investigator and any qualified designees are responsible for detecting, documenting, and recording events that meet the definition of an AE or SAE and remain responsible to pursue and obtain adequate information both to determine the outcome and to assess whether the event meets the criteria for classification as an SAE or caused the participant to discontinue the study intervention (see [Section 7.1](#)).

During the active collection period as described in [Section 8.3.1](#), each participant/legally authorized representative will be questioned about the occurrence of AEs in a nonleading manner.

In addition, the investigator may be requested by Pfizer Safety to obtain specific follow-up information in an expedited fashion.

